14.5. Secondary and Tertiary Analyses

In addition to the primary comparisons of pemafibrate treatment with placebo, prespecified secondary and tertiary endpoints will also be compared between the treatment groups. All secondary endpoints will only be evaluated if primary endpoint is positive. The total secondary endpoint alpha of 0.05 will be allocated between the secondary endpoint groups. Group A will be allocated an alpha of 0.049 and Group B will be allocated 0.001. Within each secondary endpoint group, a hierarchical testing structure will be followed based on the order of endpoints as listed below:

For the group A endpoints:

- 1. Time to first occurrence of any component of the 4-component composite endpoint of non-fatal MI, non-fatal ischemic stroke, hospitalization for unstable angina requiring unplanned coronary revascularization or cardiovascular death
- 2. Time to first occurrent of any component of the 3-component composite endpoint of non-fatal MI, non-fatal ischemic stroke, or cardiovascular death
- 3. Time to first occurrence of any component of the primary endpoint or hospitalization for HF
- 4. Time to first occurrence of any component of the primary endpoint or all-cause mortality
- 5. Peripheral artery disease, defined as incidence of lower-extremity revascularization, intermittent claudication, rest pain, lower-extremity ischemic ulceration, or major amputation with either ankle-brachial index ≤ 0.90 or other diagnostic testing (eg, toe-brachial index, angiogram, or other imaging study)

In addition to the above, an analysis of time to first occurrence of individual endpoints and an analysis of total events (evaluating time to occurrence of the first and all recurrent non-fatal MI, non-fatal ischemic stroke, coronary revascularization, or CV death) will be performed.

As a prespecified secondary analysis, evidence of any genetic effect modification that may relate to pemafibrate and incident cardiovascular events will be evaluated. In particular, whether the effect of pemafibrate as compared to placebo on cardiovascular events differs according to known genetic polymorphisms in the PPARA gene (such as, but not limited to rs6008845) will be assessed.

For the group B lipid efficacy endpoints:

- 1. The change from Screening/Enrollment Visit (Visit 1) to Month 4 Visit (Visit 5) for TG
- 2. The change from Screening/Enrollment Visit (Visit 1) to Month 4 Visit (Visit 5) for VLDL-C (calculated). VLDL-C is calculated as TC minus HDL-C minus LDL-C, where LDL-C is measured by a direct homogenous method.
- 3. The change from Screening/Enrollment Visit (Visit 1) to Month 4 Visit (Visit 5) for ApoC3
- 4. The change from Screening/Enrollment Visit (Visit 1) to Month 4 Visit (Visit 5) for ApoE
- 5. The change from Screening/Enrollment Visit (Visit 1) to Month 4 Visit (Visit 5) for HDL-C
- 6. The change from Screening/Enrollment Visit (Visit 1) to Month 4 Visit (Visit 5) for non-HDL-C (calculated)
- 7. The change from Randomization Visit (Visit 2) to Month 6 Visit (Visit 6) for non-fasting remnant cholesterol
- 8. The change from Screening/Enrollment Visit (Visit 1) to Month 4 Visit (Visit 5) for TC
- 9. The change from Screening/Enrollment Visit (Visit 1) to Month 4 Visit (Visit 5) for ApoA1

Additional analyses will separately evaluate whether the relative effects of pemafibrate versus placebo on primary and secondary endpoints is uniform over the follow-up period. These evaluations will be based on the tests for significant interactions between study time and treatments proposed by Cox,⁶⁵ as well as consideration of trends in scaled Schoenfeld residuals in the proportional hazards model. Specifically, residuals will be plotted and a significant rank correlation of residuals with time will be indicative of a changing effect.⁷¹ In the presence of significant correlation, separate effects by time period will be reported. However, even with a significant correlation of residuals with time, the best overall estimate of the effect of treatment will be the estimate obtained from the proportional hazards model without the interaction.

To assess the effect of non-informative censoring on the primary outcome, analyses will be performed following the reference-based method outlined by Carpenter, Roger, and Kenward⁶⁹ and detailed in the Statistical Analysis Plan using the piece-wise exponential method described by Lipkovich at al.⁷⁰ For those participants who were lost-to-follow-up, event status after the time of last observation is imputed using the distribution of retrieved dropouts for each arm. Retrieved dropouts are defined as participants who are no longer taking study drug but have agreed to continue to be followed. Other imputation models for missing data will also be explored for their effect on the primary outcome, including models that use the entire placebo group as the reference.

Separate proportional hazards models will also be used to compare the effects of pemafibrate treatment on time to each of the individual components of the composite primary endpoint. Analyses will use methods of competing risks survival analysis and compare the relative effects of randomized treatments on the different components of the composite outcome.^{72, 73} The approach of Lunn and McNeil⁷² provides a readily accessible implementation of a classical approach to competing risk analysis developed by Kalbfleisch and Prentice.⁷⁴

Secondary lipid efficacy endpoints will be analyzed using analysis of covariance (ANCOVA) with a retrieved dropout-based pattern mixture model. Participants with missing data will be imputed using the distribution of retrieved dropouts for each arm, where retrieved dropouts are defined as participants who are no longer taking study drug but have agreed to continue to be followed. Imputed data will be analyzed using an ANCOVA model with baseline measurement as a covariate and the treatment arm and randomization strata as fixed effects.

While all primary analyses are on the ITT population, a Per-Protocol population will also be analyzed which will be limited to participants with no major protocol deviations. Sensitivity analyses for the primary efficacy endpoint will also be conducted examining the effect of compliance and escalation of other lipid-lowering medications. Longitudinal analyses will quantify the impact of pemafibrate on lipid levels, biomarkers of inflammation, and glycemic parameters and other prespecified exploratory lipid and non-lipid biomarkers (Tertiary Endpoints: Section 5.3.1).

We will also assess whether any effects on these biomarkers mediate observed benefits or risks of pemafibrate on clinical outcomes in the study.

14.6. Subgroup Analyses

Additional planned exploratory analyses include evaluation of whether treatment effects vary across categories of baseline covariates. Key prespecified subgroup analyses will examine treatment effect by sex, prior CVD, and baseline statin use. Other subgroups of interest include region, age, race, baseline lipid levels, and other baseline biomarker levels. Within each subgroup, we will use proportional hazards models to estimate the relative rate of the primary endpoint associated with active treatment versus placebo. Both crude analyses and models including limited baseline covariates will be fitted. To test for the significance of modification of treatment effects by a baseline characteristic, we will include interaction terms between this characteristic and treatment in the proportional hazards model, with statistical significance determined by a likelihood ratio test comparing models with and without the interaction terms

Confidential K-877-302 Study Protocol

Version 3 dated 18-Mar-2020

between treatment and the categories of a specific covariate. While a formal test for heterogeneity of treatment effect by country or center has not been prespecified, center level deviations will be monitored across multiple operational quality measures such as rate of discontinuation of study drug to ensure there are no systematic differences introduced during the study.

Subgroup analyses will be conducted regardless of whether or not the overall analyses of treatment effects are significant. Our approach to interpretation of subgroup analyses has always been very cautious and recognizes that, even in large studies, it is not likely to be possible to identify reliably subgroups of participants in whom treatment is especially effective or ineffective. In the absence of prior evidence for real heterogeneity, the overall study result may provide the best evidence for the presence of a benefit in a subgroup. Our approach thus corresponds to an informal empirical Bayes procedure in which effects in an outlying subgroup require interpretation in light of the overall treatment effect.

14.7. Planned Interim Analyses

While the frequency of meetings and the approach to interim monitoring will be the choice of the DSMB, we anticipate at least twice yearly meetings to monitor recruitment and retention, with quarterly safety reports. To preserve alpha and to minimize the likelihood of an inflated effect estimate associated with early stopping, preplanned efficacy analyses will occur at accrual of approximately 50% and 75% of the planned study primary endpoints. The design of the study, including evaluation of the implications of interim monitoring on study power, considered that stopping boundaries would be based on the Haybittle-Peto method. Under this approach, the Z-values for the boundary at the 50% and 75% information times would be ± 3.29 , corresponding to 2-sided p-values of 0.001. Additionally, the DSMB will also consider the direction of effect for each of the components of the primary endpoint as well as the sensitivity analysis for loss-tofollow-up, ensuring that the point estimate for each is consistent with the composite result and there is no concern for safety. The DSMB will also consider the direction of the effect in women, again ensuring consistency with the overall result and no concern for safety. Specifically, in order for the study to be stopped early, the estimated HR for the pemafibrate group compared to placebo must be < 1 for each component of the primary endpoint as well as for the subgroup of women. Further, the HR of 1.36 seen in ACCORD⁵⁹ must not be in the 95% CI for the primary endpoint in the subgroup of women.

As a guideline for considering a recommendation to stop the study early because of convincing evidence of inefficacy (futility), preplanned inefficacy bounds will also be considered at accrual of approximately 30%, 50%, and 75% of planned study endpoints. Based upon the Linear 10% Inefficacy Boundary approach described by Freidlin, Korn, and Gray⁷⁵, the inefficacy boundary will be crossed if the observed relative hazard of the primary endpoint associated with pemafibrate assignment is greater than 1.000 at the first interim futility analysis, greater than 0.996 at the second interim futility analysis, or greater than 0.988 at the third interim futility analysis and the 95% CI excludes the expected effect. Simulations performed by Freidlin et al indicate that their Linear 10% Inefficacy Boundary approach is associated with a less than 1% loss of power due to inefficacy monitoring. Further, their approach is more conservative than a 10% or 30% conditional power approach in later follow-up (ie, after 70% of information is accrued). However, the Linear 10% Inefficacy Boundary approach is more aggressive than a

Confidential K-877-302 Study Protocol

Version 3 dated 18-Mar-2020

10% (or even a 20%) conditional power rule at earlier information accrual points, so a more conservative boundary may be preferred at the first interim futility analysis.

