14.2. Sample Size and Power

The study was designed using an event-driven approach where all participants are followed until a sufficient number of events have accrued. Regardless of the rate of major CV events in the placebo group, the study must accrue 1279 adjudicated and confirmed major CV events (with a minimum of 200 events accrued in women) in order to have 90% power to detect a 16.6% reduction in the rate with pemafibrate, based on a 2-sided test with alpha = 0.05. The sample size has been increased by 1.9% to maintain 90% power in the presence of interim monitoring. Consequently, we stipulate that the study will require accrual of 1,304 total primary events as reported in Table 6.

Using the approach of Lachin and Foulkes under the assumption of a uniform hazard we can estimate the duration of the study.⁶⁴ We will use the following assumptions:

- 1. The **recruitment will be uniform over a 30-month period**. Each randomized participant will be asked to continue blinded treatment until the study completion (when sufficient endpoints have been accrued).
- 2. Unless otherwise specified, power is set at 90% to detect the specified effect.
- 3. As these participants have strong affiliations with their treatment centers and will have been tested in a Placebo Run-In Period, low rates of loss to follow-up are anticipated. Power calculations assume a 1% annual loss to follow-up.
- 4. Sample size is assumed to be **10,000 randomized participants** (5000 receiving pemafibrate and 5000 receiving placebo).

Based on previous studies, it is anticipated that **annual event rates will be between 3.5 and 4.5 per 100 person-years** in the placebo group. We expect a higher event rate in the secondary prevention cohort (~2/3 with prior CVD) than the primary prevention cohort (~1/3 with no prior CVD). For example, a total annual event rate in the placebo group of 4.5 per 100 person-years could be achieved via an event rate of 5.2 per 100 person-years in the secondary prevention group and 3 per 100 person-years in the primary prevention group.

Under these assumptions, Lachin and Foulkes show that the power of the study with N total randomized participants in the pemafibrate and placebo groups combined is:

$$Power = \Phi^{-1}\left(\frac{\sqrt{N}|\lambda_e - \lambda_c| - Z_\alpha \sqrt{\Psi(\bar{\lambda})(Q_e^{-1} + Q_c^{-1})}}{\sqrt{2\Psi(\lambda_e) + 2\Psi(\lambda_c)}}\right)$$

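### If followed, the printed futility bounds cost 1.4 to 2.1 points of power, not under 1%, and 1,304 events then give 88.5% to 89.2% power rather than 90%

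*Protocol*

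**What the plan says.** Protocol 14.7, repeated in SAP 5.2, plans futility looks at about 30%, 50% and 75% of the planned primary events. The boundary is crossed if the observed relative hazard is "greater than 1.000 at the first interim futility analysis", above 0.996 at the second look, or above 0.988 at the third. The sentence then ends "and the 95% CI excludes the expected effect". It does not say which looks that condition governs or what value the expected effect takes.

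The justification cites simulations in the paper that proposed the Linear 10% Inefficacy Boundary. According to these, the "approach is associated with a less than 1% loss of power due to inefficacy monitoring". No power loss is reported for this trial's own bounds and look times. The same paragraph calls the rule a guideline. It adds that the rule is more aggressive early on than a 10% or even 20% conditional power rule, and that something more conservative may be preferred at the first look.

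On power, Protocol 14.2 says "the study must accrue 1279 adjudicated and confirmed major CV events" for "90% power to detect a 16.6% reduction in the rate with pemafibrate", "based on a 2-sided test with alpha = 0.05". It continues: "The sample size has been increased by 1.9% to maintain 90% power in the presence of interim monitoring". Hence "the study will require accrual of 1,304 total primary events as reported in Table 6".

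**The concern.** A DSMB reading section 14.7 finds one number for what futility stopping costs, and that number is below 1%. Section 14.2 tells it that 90% power survives interim monitoring. If the bounds cost more than that at this trial's looks, both statements mislead anyone deciding how firmly to apply the guideline. The decision most affected is the 30% look. There, stopping on an observed hazard ratio just above 1 could end a trial of a drug that has the full design effect. The unclear confidence-interval condition adds a practical difficulty: an observed hazard ratio of 1.01 at that look may or may not count as a crossing.

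**Working it through.** **Inputs.** From Protocol 14.2: two-sided alpha 0.05, 90% power, hazard ratio 0.834, 1:1 allocation, 1,279 events raised by 1.9% to 1,304. From Protocol 14.7: efficacy looks at 50% and 75% with |Z| > 3.29; futility looks at 30%, 50% and 75% (391, 652 and 978 events). The standard error of the log hazard ratio is taken as 2/√d for d events.

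**Reproducing the plan's event count.** With ln 0.834 = −0.1815, the Schoenfeld formula gives d = 4(1.960 + 1.282)²/0.1815² = 1,276, and Freedman's gives 1,283. The stated 1,279 lies between them. 1,279 × 1.019 = 1,303.3, which rounds up to 1,304. Fixed-sample power is Φ(0.1815·√d/2 − 1.960), which is 90.1% at 1,279 and 90.6% at 1,304. Adding the two efficacy looks leaves it at 90.6%. The plan's figures are therefore confirmed when only efficacy monitoring is counted.

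**The confidence-interval condition.** The 95% CI excludes an expected hazard ratio h only if the observed value exceeds h·exp(1.96 × 2/√d).

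| Look | Printed bound | CI threshold, h = 0.834 |
|---|---|---|
| 30% (391 events) | 1.000 | 1.017 |
| 50% (652 events) | 0.996 | 0.972 |
| 75% (978 events) | 0.988 | 0.945 |

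With h = 0.834 the condition changes only the first look. An observed 1.000 at 391 events has a lower limit of exp(−1.96 × 0.1011) = 0.820, which does not exclude 0.834. With h = 0.82 or 0.80 the first-look threshold is 0.9997 or 0.975, so the printed 1.000 governs. It also governs if the condition belongs to the third look only.

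**Power at 1,304 events, true hazard ratio 0.834, bounds followed whenever crossed.** These figures come from recursive numerical integration of the group-sequential process with a final critical value of 1.96. A simulation of 4 million paths agrees.

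| Rule | Power | Loss (points) |
|---|---|---|
| Efficacy looks only | 90.6% | – |
| Hazard-ratio bounds alone (also: CI condition at look 3 only, or h = 0.82 or 0.80) | 88.5% | 2.13 |
| CI condition at all looks, h = 0.834 | 89.2% | 1.44 |
| First futility look not used | 90.3% | 0.28 |

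In relative terms the two losses are 2.4% and 1.6%, so both exceed 1% whichever way loss is defined. Adjusting the final critical value to 1.962 changes the losses by less than 0.01 point.

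**Where the loss arises.** Under 0.834, the chance of crossing at the first look is 1 − Φ(0.1815/0.1011) = 3.6% with the bound at 1.000, and 2.5% at 1.017. Just over half of the trials stopped there would otherwise have reached significance.

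**Events that would be needed.** To hold 90% with the guideline followed takes about 1,347 events (CI condition at all looks) to 1,375 (hazard-ratio bounds alone). That is 5.3% to 7.5% above 1,279, against the 1.9% allowed.

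**The case against.** Several points on the other side are sound.

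- The figure below 1% is attributed to the cited paper's simulations. The plan does not say it was computed for these bounds, and the paper's conditions cannot be checked from these documents. A reader might infer that the paper is wrong or that the plan made a false calculation; neither is shown. What stands is that this is the only cost the plan sets beside its own bounds, and it is not true of them at 30%, 50% and 75%.
- Protocol 14.7 says the evaluation of monitoring and power assumed Haybittle-Peto boundaries, so the 1.9% may have been meant for the efficacy looks alone. On that reading 90% holds, at 90.6%. But section 14.2 refers to interim monitoring without that limit.
- The rule is a guideline and the approach to monitoring is left to the DSMB. The text itself flags the first look as aggressive. This makes the loss conditional. It does not supply a trial-specific cost or an alternative bound, and non-binding status does not restore power if the guideline is followed.
- The shortfall from 90% is only 0.8 to 1.5 points.

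A reader might also infer that the CI condition makes the printed 1.000 a dead letter, and that this is why power falls. The first part depends on one reading of an ambiguous sentence. The second is backwards: if the condition does override 1.000, the loss shrinks from 2.1 to 1.4 points.

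**Conclusion.** The point holds in a conditional form. If the futility guideline is followed at a true hazard ratio of 0.834 and 1,304 events, the loss is 1.4 to 2.1 points and power is 89.2% to 88.5%, depending on how the CI condition is read. No reading examined gives a loss under 1 point, so the 1.9% increase does not preserve 90% power in that case. Nearly all of the loss is due to the 30% look. The result assumes proportional hazards, looks at exactly 30%, 50% and 75% of 1,304 events, and stopping whenever a bound is crossed. It does not show that the trial is underpowered if the DSMB sets the first look aside: power is then 90.3%. This is a correction to a stated figure and an ambiguous clause, of modest size.

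**What to change.** 1. In Protocol 14.7, SAP 5.2 and the DSMB charter, replace or supplement the cited figure with this trial's own: a loss of 1.4 to 2.1 points, and power of 88.5% to 89.2% if the bounds are followed. Narrow the range to one value once item 2 is settled.
2. State which looks the CI condition covers and which hazard ratio is the expected effect, so that each look has one operative threshold.
3. In Protocol 14.2 and SAP 4.3.1, say whether the 1.9% increase allows for the efficacy looks only.

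These are wording changes and need no added participants or events.

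Optionally, use the latitude the text already gives and set a more conservative first bound, leaving the other two unchanged. A first bound of 1.05 gives 89.9% power, and about 1.06 gives just over 90.0%. The price is a lower chance of stopping an ineffective drug early. Under a true hazard ratio of 1.00, crossing at the first look falls from 50% to 31% (1.05) or 28% (1.06). Crossing at any look falls only from 71% to 67% or 66%, because the later looks recover most of it.

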15. DIRECT ACCESS TO SOURCE DATA/DOCUMENTS

15.1. Study Monitoring

PROMINENT will be coordinated through an academic-industry partnership between investigators in the CCVDP at the Brigham and Women's Hospital and Harvard Medical School (Boston, US) and Kowa Research Institute, Inc., or its designees. The study structure will include a Scientific Advisory Committee (SAC) with specific knowledge of PPAR-α biology and with responsibilities including the evaluation and amendment of the study design before launch; a study Steering Committee (SC) to include members from all participating countries; an EC with responsibilities for the overall enrollment, conduct, and completion of the study; an OC with responsibilities for daily management and interactions with the study Contract Research Organization (CRO), central laboratory, biorepository, and drug dispensary; a blinded CEC; a DCC; and a fully independent DSMB.

Monitoring visits will be conducted according to all applicable regulatory requirements and standards. It is understood that the monitor will contact and visit the investigator regularly and will be allowed, to inspect the various records of the study. It will be the monitor's responsibility to inspect the eCRFs at regular intervals throughout the study to verify adherence to the protocol and the completeness, accuracy and consistency of the data; and adherence to the International Council for Harmonisation (ICH) GCP and local regulations on the conduct of clinical research. The monitor should have access to laboratory reports, study medication, records associated with it, and other medical records needed to verify the entries on the eCRF.

